will occur +/- 7 days from the expected date based on the baseline study visit. The post study (month 6) will occur +/- 7 days from the expected date based on the baseline study visit. A member of the study team will contact the subject each month to coordinate fecal sample transport to UTMB, check for adverse events and overall well-being, and ensure compliance and ongoing consent. If the mTBI subject sustains and additional TBI during the study, the study for both the mTBI and household control subject will be extended to collect monthly fecal samples and questionnaires for an additional 6 months.

mTBI Group (Arm 2)

Before and at completion (month 6) of the rhGH intervention, mTBI subjects will report to the UTMB Institute for Translational Sciences (ITS) Clinical Research Center (CRC) for testing, which will consist of cognitive function assessment (MoCA), determination of lean mass and fat mass using DEXA, resting energy expenditure, functional testing including leg strength and 6 minute walk test, fatigue measurements, and questionnaires of mood and quality of life, gastrointestinal health, sleep, and food preferences. Blood sampling for measurement of amino acid levels, hormones, and metabolites will be drawn before and 90 minutes (+/- 10 minutes) after a standardized meal. In addition, fecal samples for analysis of the GI microbiome will be collected monthly for the duration of the study. Insulin Growth Factor 1 (IGF-1) levels will be monitored at a month 1 safety visit for all mTBI subjects. The month 1 safety visit will occur +/- 5 days from the expected date based on the baseline study visit. The monthly fecal sampling will occur +/- 7 days from the expected date based on the baseline study visit. The month 6 post study will occur +/- 7 days from the expected date based on the baseline study visit. A member of the study team will contact the subject each month to coordinate fecal sample transport to UTMB, check for adverse events and overall well-being, and ensure compliance and ongoing consent. If the mTBI subject sustains and additional TBI during the study, the study will be extended to collect monthly fecal samples and questionnaires for an additional 6 months. Genotropin will be provided for the additional 6 months.

Healthy control group (Arm 2)

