analysis of the GI microbiome will be collected monthly for the duration of the study. Insulin Growth Factor 1 (IGF-1) levels will be monitored at a month 1 safety visit for all PASC subjects. The month 1 safety visit will occur +/- 5 days from the expected date based on the baseline study visit. The fecal sampling will occur +/- 7 days from the expected date based on the baseline study visit at months 0, 1, 2, 3, 4, 5, 6, 9 and 12. The month 6 study will occur +/- 7 days from the expected date based on the baseline study visit. The month 9 study will consist of fecal sample and questionnaires only. At month 12, the subject will return to the ITS-CRC to repeat the glucagon stimulation test (GST). Questionnaires and a fecal sample will also be collected at this time. A member of the study team will contact the subject each month to coordinate fecal sample transport to UTMB, check for adverse events and overall well-being, and ensure compliance and ongoing consent. If a PASC subject is infected with COVID again during the study months 9 - 12, the study will be extended to collect fecal samples and questionnaires for an additional 3 months.

Therapeutic Intervention (for mTBI subjects only - Arms 1&2; PASC subjects – Arm 3). Recombinant human growth hormone (rhGH), (GENOTROPIN). Growth hormone (GH) is produced endogenously by the body and is released by the pituitary. Therapeutic rhGH is FDA approved for clinical use for replacement of endogenous growth hormone in children and adults with growth hormone deficiency. GENOTROPIN, the agent to be used in this study is manufactured by Pfizer Inc and contains somatropin, which is a polypeptide hormone of recombinant DNA origin. It contains 191 amino acid residues and is identical to human growth hormone of pituitary origin.

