- Montreal Cognitive Assessment (MoCA). The Montreal Cognitive Assessment (MoCA) (20) is a rapid assessment of cognition. The MoCA consists of 9 questions with the following subcategories: visuospatial/executive, naming, memory, language, abstraction, delayed recall and orientation. The MoCA has been used extensively to detect cognitive impairment in many conditions, including head trauma. Version 7.1 will be used at the Month 0 testing and Version 7.2 will be used at the Month 6 testing.

GI microbiome. The GI microbiome will be assessed using fecal samples collected at monthly time points (baseline (month 0), month 1, month 2, month 3, month 4, month 5, and month 6). Additional fecal samples will be collected for Arm 3 PASC subjects at month 9 and month 12. If a mTBI subject sustains an additional TBI during the study period, the study will be extended to collect fecal samples for an additional 6 months. If a PASC subject is infected with COVID again during the study months 9 - 12, the study will be extended to collect an additional sample at month 13 and month 15. Subjects will provide fecal samples as described below. Fecal samples will be collected +/- 7 days from specified time point based on baseline (month 0) study. Subjects will be allowed to collect monthly fecal samples at home. Samples will be stored at 4°C until transferred to UTMB (on/+ 3 days after collection). Subjects will be given a tutorial on how to properly collect the fecal sample. They will be given a handout from the manufacturer of the collection kit with step by step instructions. They will also be shown a video of the collection process supplied by the kit manufacturer. https://www.youtube.com/watch?v=ytr_hmJdHqM&feature=youtu.be&rel=0

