An additional collection will be performed at month 0 and month 6 to collect viable fecal material. Fecal samples will be collected using the spatula included in the OMNIgene-Gut kit used in the first collection. Briefly, after the participant will transfer fecal material to the yellow top of the collection tube for the first collection, then they will scoop another small amount of fecal material with the same spatula and transfer it to a prepared cryogenic freezer tube containing sterile PBS (without Ca/Mg) and sterile glycerol. The tube will be closed and shaken for a minimum of 30 seconds to mix with the stabilization liquid. Samples will be labeled with the subject's unique code and stored at 4°C until transported to University of Texas Medical Branch. Samples will then be frozen at -80°C and stored until the molecular analysis is complete. After initial analysis, if the sample is considered useful (representative of the average BIAFAC subject), it may be thawed, diluted in saline and used either to mix in a mathematical ratio to create a synthetic community or to be directly transplanted into germ free mice. If the sample is considered not useful (not representative of the average BIAFAC subject) for fecal microbiome transplant into germ free mice, the sample will be destroyed.

- Nasal Microbiome – Arm 3 only. A nasal swab will be performed by research staff or by the subject under direction of the research staff. The sterile calcium alginate swab will be inserted into the left nare until resistance is met, rotated 5 times and then moved to the right nare and rotated 5 times. The swab will be immediately placed in a tube containing MagNAPure lysis buffer. The shaft of the swab will be snapped off and discarded leaving the head of the swab immersed in the lysis solution. The tube cap will be tightly secured and the tube will be shaken for a minimum of 5 seconds to saturate the head of the swab with the lysis buffer releasing the bacterial lysate into the fluid. Samples will be stored at -80C for subsequent batch DNA extraction on a MagNAPure96 followed by microbiome profiling by NGS and/or qPCR. Samples will be labeled with the subject's unique code. This outcome measure will be performed at baseline (month 0) and post (month 6) to address anosmia/dysosmia common in PASC subjects and to determine if exogenous GH impacts the nasal mucosa/microbiome .

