- Food Preference Questionnaire (FPQ). General food preferences will be assessed using a modified questionnaire. The food preference questionnaire requires participants to rate their liking of 62 individual foods on a 5-point Likert scale, ranging from “not at all” to “a lot”. Participants are instructed to select ‘N/A’ if they are not familiar with - or have no memory of - having tried a food item. Food preference scale scores for six food categories (Vegetables, Fruit, Meat/Fish, Dairy, Snacks, and Starches) are obtained by summing the single food preference item scores within each food category and dividing this sum by the number of items on the list. FPQ will be measured at month 0 and month 6 by TBI subjects. PASC subjects complete the FPQ at months 0, 6, 9 and 12. If a mTBI subject sustains an additional TBI during the study period, the study will be extended for an additional 6 months. An additional questionnaire will be collected at the end of the 6 month period. . If a PASC subject is infected with COVID again during the study months 9 - 12, the study will be extended to collect an additional questionnaires at month 13 and month 15.
- Gastrointestinal Symptom questionnaire. Gastrointestinal symptoms will be monitored monthly using the Gastrointestinal Symptom Rating Scale (GSRS). The GSRS is a 15-item questionnaire. Each question has a seven-point Likert-type scale where 1 represents absence of symptoms and 7 represents very troublesome symptoms. The GSRS will be measured each time a fecal collection is completed. If a mTBI subject sustains an additional TBI during the study period, the study will be extended for an additional 6 months. The GSRS will be collected monthly during the 6 month extension. . If a PASC subject is infected with COVID again during the study months 9 - 12, the study will be extended to collect an additional questionnaires at month 13 and month 15.

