- Recombinant Human Growth Hormone Administration. mTBI and PASC subjects will be asked to inject themselves with growth hormone daily. The starting dose will be 0.4 mg/day beginning at the baseline study and will increase to 0.6 mg/day when instructed by the study team. The dose increase will happen after the month 1 IGF-1 blood draw and the study team reviews the results and instructs the subject to increase their dose to 0.6 mg/day. TBI subjects will administer growth hormone for 6 months. PASC subjects will administer growth hormone for 9 months. If a mTBI subject sustains an additional TBI during the study period, the study will be extended for an additional 6 months. Genotropin will be provided for the additional 6 months at a dose of 0.6 mg/day.
- Glucagon stimulation test. Arm 3 PASC subjects will have a glucagon stimulation test at month 12. After the IV is placed, 3.5 ml of blood will be collected for the baseline (time: 0 minutes) to test for levels of human growth hormone. 1 mg glucagon (for subjects over 90 kg, 1.5 mg glucagon) will be injected IM in the deltoid muscle of the subject. Additional blood samples (3.5 mL) will be collected to test for levels of human growth hormone at time points: 90 minutes, 120 minutes, 150 minutes, and 180 minutes. All blood samples will be sent to UTMB clinical laboratory for analysis and entered into subjects UTMB medical chart.

Study Procedures for household and healthy control subjects.

Household controls will complete the procedures below. Differences in procedures between Arm 1 and Arm 2 will be noted.

- Vital signs. Vital signs will be collected at all study visits. This will include height, weight, blood pressure, pulse, respirations, and temperature. Vital signs will be recorded on the appropriate study visit CRF.
- Blood draw. Subjects will have blood drawn at the baseline (month 0) and post (month 6) visits. Blood will be drawn using a butterfly needle from a peripheral vein in the arm. Subjects will be fasted for at least 10 hours.
 - Baseline Visit (Month 0):
Up to 15 ml of blood (1 serum separator top (5ml); 1 lithium heparin (6ml); 1 K-EDTA (4ml)) will be collected from fasted (at least 10 hours) subjects for analysis of hormones, amino acids and metabolites. In addition, up to 13ml of blood (1 serum separator top (5ml); 1 lithium heparin (6ml)) will be collected after a standardized meal for the analysis of amino acids.
 - Post Visit (Month 6):

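### The month-0 stool window in Arm 3 (and possibly Arms 1 and 2) runs 7 days past the start of rhGH, so a baseline sample can be post-dose and still in protocol

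*Combined protocol and SAP*

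**What the plan says.** The Arm 3 text under Experimental Protocol, PASC Group, reads: "The fecal sampling will occur +/- 7 days from the expected date based on the baseline study visit at months 0, 1, 2", followed by the remaining months to 12. Month 0 is named, and the window runs both ways.

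For Arms 1 and 2 the text is less direct. Their own sections say only: "The monthly fecal sampling will occur +/- 7 days from the expected date based on the baseline study visit", without naming month 0. The GI microbiome item under Study Procedures, which covers all three treated arms, lists month 0 among its time points ("The GI microbiome will be assessed using fecal samples collected at monthly time points (baseline (month 0), month 1, month 2", and so on to month 6). It then states: "Fecal samples will be collected +/- 7 days from specified time point based on baseline (month 0) study". It makes no exception for month 0.

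On the start of treatment, the rhGH administration item says: "The starting dose will be 0.4 mg/day beginning at the baseline study". Injections are daily.

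Three further provisions matter:
- Home collection: "Subjects will be allowed to collect monthly fecal samples at home".
- The GI symptom questionnaire follows the stool date: "The GSRS will be measured each time a fecal collection is completed".
- The viable sample is taken at the same time points: "An additional collection will be performed at month 0 and month 6 to collect viable fecal material".

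**The concern.** The month-0 sample is the reference for most of the trial. Aims 1a and 2 compare it with controls, Aim 1b compares Prevotella-positive with Prevotella-negative mTBI subjects at baseline, and Aim 3 uses the change from it to month 6. The background section also makes each participant's baseline that participant's own control.

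If the window opens 7 days before the baseline visit and closes 7 days after it, and treatment begins at that visit, the second half of the window falls on treatment. Controls receive no rhGH, so only the treated side of the comparison is exposed.

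The direction follows from the plan. Under Aim 1a, Statistical Considerations expects GH to remove the mTBI-control difference. The background section asks whether GH moves mTBI and PASC microbiomes toward those of healthy controls. If that is so, a post-dose baseline already contains part of the shift, and both the baseline contrast and the measured change to month 6 come out too small.

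**Working it through.** **Timing.** With the first injection on day 0 and one injection a day, a stool on day +7 follows the injections of days 0 to 6, which is 7 doses (8 if that day's injection came first). The explicit window covers the 25 Arm 3 subjects out of 75 treated (25 + 25 + 25).

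**Does other text close the gap?** Four places point to a pre-treatment sample:
- The arm sections put the GI-health questionnaire in the testing done before rhGH. Fecal sampling is then added in a separate sentence with its own window.
- Figure 3 lists fecal sampling in the month-0 baseline box, without ordering it against the first dose.
- The payments include no separate month-0 collection: 50 + 2×150 + 5×25 + 6×25 = 625 dollars (mTBI) and 50 + 2×150 + 50 + 6×25 + 9×25 = 775 dollars (PASC), matching the stated totals.
- Aim 1a in Statistical Considerations calls the time point PRE.

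None of them places the stool before the first injection.

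**The plan's own power figure.** Two-sample t-test, two-sided alpha 0.05, noncentral t. The stated effect size d = 1.184 for Alistipes onderdonkii gives 70.7%, 87.9%, 95.4% and 98.4% at 10, 15, 20 and 25 per group, as in the protocol table. For Odoribacter, d = 0.956 (solved from the stated 91.2% at 25 per group) also returns the stated 71.5% and 83.8% at 15 and 20 per group.

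**Illustrative size.** The documents give neither a rate of microbiome change under rhGH nor a share of late samples, so both are assumed. Let g(t) be the fraction of the group difference already removed by day t, with full removal at day 182:
- linear onset: g(t) = t/182
- exponential onset: g(t) = (1 − exp(−t/τ)) / (1 − exp(−182/τ))

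Late samples are spread evenly over days 0 to 7. Average loss = share late × mean of g over those days, and d is multiplied by (1 − average loss). Collection spread evenly from day −7 to day +7 would make half of the samples late.

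| Onset | Mean g, late samples | Average loss, 10% late | Average loss, half late | Odoribacter power, 10% late | Odoribacter power, half late |
|---|---|---|---|---|---|
| Linear | 1.9% | 0.2% | 1.0% | 91.1% | 90.7% |
| τ = 90 d | 4.4% | 0.4% | 2.2% | 91.0% | 90.0% |
| τ = 60 d | 5.9% | 0.6% | 2.9% | 90.9% | 89.5% |
| τ = 30 d | 10.8% | 1.1% | 5.4% | 90.6% | 88.0% |
| τ = 14 d | 21.3% | 2.1% | 10.7% | 90.0% | 84.1% |

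The powers are at 25 per group, which is the Aim 2 comparison, and carry TBI effect sizes over to PASC as the protocol does. On the same basis Alistipes falls from 98.4% to 98.4%–98.0% (10% late) or 98.2%–95.6% (half late).

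For Aim 1a with 50 per group, the 10.7% loss takes Odoribacter from 99.7% to 98.8%, and Alistipes stays at 99.9% or more. All eight organisms with stated power of at least 91% stay at or above 98.8%. If the Arm 1 and 2 window does not cover month 0, the Aim 1a loss is zero.

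**The case against.** The strongest reply is that the combined text already points to a pre-treatment stool. The GI questionnaire belongs to pre-rhGH testing and is completed with each stool, so the two together tie the stool to that testing. Month 0 is also the anchor of the window, and it may have entered the Arm 3 list only because that arm's schedule is not monthly after month 6. This settles the intent, but it does not change the written rule, under which a sample on day +5 is not a deviation.

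The second reply concerns size, and it stands. The 84.1% figure needs half of the subjects late, a 14-day onset constant and complete normalisation by month 6, none of which the documents support. The powers also use an unadjusted alpha of 0.05, although the plan intends multiplicity corrections.

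A reader might infer more than the text supports:
- **That the window is explicit for all treated subjects.** It is explicit for Arm 3 only. For Arms 1 and 2 it is a reading of the general procedure.
- **That late baselines could produce false positives.** Under the plan's hypothesis the baseline contrast and the change are biased toward no effect.
- **That a separate first-injection date is indispensable.** Dosing is stated to start at the baseline study, so the stool date and the visit date identify late samples unless the first injection was on another day.
- **That one added clause would close the gap.** Several sections need aligning, and a window opening at day −7 would conflict with the 3-day transfer limit, because stools from days −7 to −4 could not wait for the visit.

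**Conclusion.** The point holds as a minor one. For Arm 3 the written rule allows a baseline stool, with its GSRS and viable sample, to follow up to about 7 rhGH doses. For Arms 1 and 2 the general procedure can be read the same way. The rule permits this; nothing shows that it happens, or how often.

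The expected effect is a small bias toward no effect in the baseline contrasts of Aims 1a and 2 and in the change from month 0. That direction depends on the plan's own hypothesis. For Aim 1b both groups are treated, so the direction is not determined. The effect on the Aim 3 correlation was not derived. The size cannot be computed from the documents. The losses above, 0.2% to 2.1% of the baseline difference with 10% late and 1.0% to 10.7% with half late, illustrate the assumptions and are not estimates. A correction is worth making because it is cheap and the sample is the trial's reference point.

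**What to change.** In the Arm 3 text and the GI microbiome procedure, and for consistency in the Arm 1 and Arm 2 text, replace ±7 days at month 0 for treated subjects. Require the month-0 samples (OMNIgene and viable) on or before the baseline visit and before the first rhGH injection. Choose a pre-visit window that fits the 3-day transfer limit: a stool brought to the visit can be at most 3 days old. Keep ±7 days for later months. Controls need no change on this account.

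Record the stool collection date, and the first-injection date if it differs from the baseline visit. Collection dates may already be in the laboratory specimen records listed under Precautions for Maintaining Data Integrity. Repeat the baseline and change analyses without any month-0 sample taken after the first injection; this also deals with samples already collected. Treat a subject with no pre-dose stool as having a missing or flagged baseline sample. Dosing does not change.

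Cost: edits to these sections and the collection handout, one or two dates on the case report form, and one sensitivity analysis. Kits must be handed out before the baseline visit, and a few baseline samples may be missing or flagged. Sample size and alpha are unaffected.
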